## HYPOTENSION\*\* TREATMENT PROTOCOL

Group CM	Group HPI

First hypotensive episode:
 
 
• 500mL IV bolus
 
• Ephedrine 10mg IVP (unless otherwise specified by physician anesthesiologist of record)
 
 
Second hypotensive episode:
 
 
• Ephedrine 10mg IVP (unless otherwise specified by physician anesthesiologist of record)
 
 
Third hypotensive episode:
 
 
• Physician anesthesiologist of record discretion
 
	
First HPI alert /First hypotensive episode:
 
 
• Look at hemodynamic relations screen
 
• If it is a preload issue, give 500mL IV bolus
 
• If it is a contractility or afterload issue, give Ephedrine 10mg IVP (unless otherwise specified by physician anesthesiologist of record)
 
 
Second HPI alert /Second hypotensive episode:
 
 
• Look at hemodynamic relations screen
 
• If it is a preload issue, give 500mL IV bolus
 
• If it is a contractility or afterload issue, give Ephedrine 10mg IVP (unless otherwise specified by physician anesthesiologist of record)
 
 
Third HPI alert /Third hypotensive episode:
 
 
• Physician anesthesiologist of record discretion
 

### \*\*Hypotension as defined above

**Key:** **MAP:** mean arterial pressure; **CM:** conventional monitoring (standard care); **HPI:** hypotensive prediction index group (ClearSight device and algorithm); **BP:** blood pressure; **SBP:** systolic blood pressure; **NIBP:** non-invasive blood pressure; **IVP:** Intravenous push

e. **Electronic Health Record Variables Collected:**

- Age
- Race/Ethnicity
- Insurance status
- Gravidity
- Parity
- Estimated gestational age
- Body mass index
- Induction vs Spontaneous Labor
- Last known cervical exam at the time of ELA initiation
- Pain score immediately prior to ELA initiation
- Total vasopressor doses from time of ELA initiation until delivery
- Time of hypotensive event start to time of treatment for hypotension
- Changes in fetal heart rate Yes/No
  - If Yes: Time, in minutes, from ELA initiation until category change detected
- Presence or absence of fetal heart rate decelerations within 1 hour of initiation of ELA (yes/no)
- Mode of delivery
- Neonatal weight
- Neonatal Apgar scores
- Neonatal cord blood pH

3. **Risks/Benefits:**

Benefits

Close monitoring and treatment of hypotension

Risks

Loss of confidentiality

Discomfort with devices

Inconvenience answering questions

Risk of obtaining a false positive reading and being given fluids or other management of blood pressure that was not necessary.

4. **Data Analysis:**

a. **Data collection form:** See Appendix

b. **Statistical Analysis Plan**

Descriptive statistics will be calculated for variables and compared between groups. We will report mean  $\pm$  SD for normally distributed continuous data; median (interquartile range) for data not normally distributed or for data with outliers or ordinal data; and number (percentage) for categorical data. Kolmogorov–Smirnov test will be applied to test for normality of data distribution. An unpaired two-tailed t test will be used for comparing parametric data between groups, and Mann–Whitney U and Wilcoxon rank sum tests will be used for nonparametric data. The chi-square test or Fisher exact test will be applied as appropriate for comparing proportions between groups.  $P < 0.05$  will be considered statistically significant.

*Primary Outcome Analysis (Survival Analysis)*

Single-variable proportional hazards regression models will be created for each potential covariate of interest. Time-to-event estimates  $+$ /SE for both groups will be calculated from the single-variable models. Using  $P < 0.10$  from the univariate models as a threshold for inclusion in the multivariable model, the best-fit multivariable model will then be generated by removing variables with  $P > 0.05$  from the multivariable model in a backward stepwise fashion. To assess the primary outcome regarding relationship between treatment groups and “survival” (treatment-free) time, a proportional hazards model will be used to assess the effect of the monitoring type, with effects of covariates controlled in the best-fit multivariable model.

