Our proposed solution involves using the hypotension prediction index (HPI, ClearSight, Edwards Lifesciences, Irvine, USA) to reduce time-to-treatment of epidural labor analgesia (ELA)-associated hypotension. The HPI algorithm on ClearSight uses arterial waveform features to predict hypotension, defined by mean arterial pressure (MAP) < 65 mmHg for at least 1 minute. The index ranges 0 to 100 with higher numbers reflecting a higher likelihood of subsequent hypotension. HPI has 92% sensitivity and specificity for predicting hypotension 5 min in advance, sensitivity 89% and specificity 90% for 10 min in advance and 88% and 87% for 15 min in advance. The sensitivity and specificity of HPI to accurately predict hypotension has also been validated with conventional invasive and non-invasive arterial waveforms, in both pregnant and non-pregnant cohorts. Other studies have similarly demonstrated the effectiveness of HPI in predicting hypotension in perioperative settings. The algorithm is approved for sale in Europe and the United States. To our knowledge, no study to date has rigorously assessed the utility of HPI in ELA compared to conventional monitoring, for the benefits of reduced time-to-treatment of ELA-associated hypotension.

This trial will investigate the ease of use and feasibility of the ClearSight monitoring system in comparison to the Conventional blood pressure monitor (upper arm cuff) during and after epidural-labor analgesia

placement. The pilot study will compare time-to-treatment of hypotension between conventionally monitored patients (Group CM) and those receiving HPI (Group HPI) monitoring by ClearSight, in a population of healthy people receiving ELA, and with the intent to expand this pilot study to a larger population of women to meet the power required to identify difference in time to treatment for hypotensive events.

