## III. Investigational Plan

### 1. **Study design:** Prospective randomized controlled trial

### 2. **Methods:**

a. **Size of study groups(s):** The primary outcomes are 1.) ease and feasibility of use of the ClearSight monitoring system during labor and delivery, post-epidural-labor analgesia placement; and 2.) time-to-treatment of hypotension, defined as MAP <65 mmHg for more than 1 minute. Our initial pilot sample is expected to identify the ability to use the ClearSight monitoring in the labor and delivery suite, the patient adherence to the finger cuff monitors, and the feasibility of hypotension detection at the central monitors. The pilot sample (N = 30) is not expected to demonstrate significant differences in the relation between mode of blood pressure measurement and time-to-treatment of hypotension but should yield an estimate of the potential differences for a continuance of study.

b. **Environment and Estimated timeline to sample size acquisition:** UPMC Magee performs about 7,400 ELA annually, a range of 20-30 ELA daily. Based on a meta-analysis of trials, the estimated incidence of hypotension after initiation of neuraxial analgesia during labor is approximately 19% (range: 3-35%). Our internal data that shows approximately 20-30% of patients receiving ELA require treatment with a vasopressor within the first 4 hours of ELA initiation; we will use the conservative estimate of 20%. Our internal experience with similar trials also informs our timeline: in our prior experiences with similar labor and delivery trials we have achieved a consistent approach-to-recruit ratio of about 25%. Based on our volume, ELA utilization, eligibility criteria, and rates of ELA-associated hypotension, we estimate a total of 5-8 weeks of recruitment. A total of N=30 patients will be enrolled with a predicted 20% (n=6) experiencing hypotension events of interest.

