### c. **Outcomes:**

Primary outcome:

Ease of use of ClearSight blood pressure monitoring system

(0 – 10) Ratings from patient and patients' assigned nurse during ELA

Feasibility of blood pressure monitoring (yes/no response from assigned nurse regarding patient care.

Time-to-treatment of hypotension (minutes)

Secondary outcomes: (only exploratory)

Total time in hypotension with MAP <65 mmHg

Nausea

Vomiting

Total phenylephrine, mg

Total ephedrine, mg

Total intravenous fluids, mL  
Changes in fetal heart rate category  
Presence or absence of fetal heart rate decelerations within 1 hour of initiation of ELA  
CO, CI, SV, SVV

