**e. Protocol specific methods:**

Patients will be screened electronically using the electronic health record upon arrival at the Womancare birth center at UPMC Magee. Patients are eligible if they are pregnant, admitted for labor and delivery, and receiving ELA. If patients are undecided about whether they will receive ELA but are interested in the research, they may be consented and then marked as a "screen failure" if they do not receive ELA. These patients will not be randomized. Patients who receive ELA will be randomized to treatment of hypotension according to conventional monitoring (Group CM) or monitoring by HPI (Group HPI). Randomization will be 1:1 and occurs immediately after informed consent and signature for research activities. Subjects will be informed of their assignment after all research activities and data collection have been completed. Total monitoring time will be 4 hours starting from the initiation of ELA. To enable group comparisons of total time in hypotension, all participants will wear ClearSight and a Conventional Monitoring cuff; Group CM will be blinded to ClearSight output and receive standard care for the treatment of hypotensive events post-epidural-labor analgesia. Group HPI will receive treatment of hypotension according to ClearSight output and specified by the hypotension treatment protocol below.

Clinical research staff who have been trained in ClearSight will apply the device and troubleshoot any problems. Providers will be trained on the monitor, its interpretation, and output, prior to study launch and real time at the time of active study participant enrollment. This training applies only to those participants who will receive non-blinded treatment assignment

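### Ease and feasibility of ClearSight, the first primary outcome, has no analysis, interval or pre-specified benchmark of its own, and the default between-group test does not measure usability

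*Combined protocol and SAP*

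**What the plan says.** III.2.a (Size of study groups) names two primary outcomes. The first is "ease and feasibility of use of the ClearSight monitoring system during labor and delivery, post-epidural-labor analgesia placement"; the second is time-to-treatment of hypotension. III.2.c (Outcomes) gives the measures: "Ease of use of ClearSight blood pressure monitoring system", rated 0 to 10 by the patient and the assigned nurse, and "Feasibility of blood pressure monitoring (yes/no response from assigned nurse regarding patient care". Neither section attaches a target value.

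In III.4.b the part headed Primary Outcome Analysis is a proportional hazards model for treatment-free time. The Secondary Outcome Analyses list does not include ease or feasibility. The only text that reaches them is the opening paragraph of III.4.b: "Descriptive statistics will be calculated for variables and compared between groups". It calls for means, medians or percentages according to the type of data, then t, rank, chi-square or Fisher tests between groups, with P<0.05 as the significance level.

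Three other statements bear on the point:

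- III.2.e (Protocol specific methods) has every participant wear both ClearSight and the arm cuff, with Group CM blinded to ClearSight output.
- III.2.d excludes anyone who cannot use ClearSight, for whatever reason, and anyone with incomplete data.
- II.1 (Background) describes the study as a pilot "with the intent to expand this pilot study to a larger population of women to meet the power required".

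**The concern.** Whether a device is usable is a question of level: is the proportion of yes answers, or the rating, high enough? A test between two groups that both wear the device asks whether the level differs by group. A device that fails in half the patients of each group and one that works in nearly all of them would usually give the same test result.

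This matters because III.2.a concedes that 30 patients are not expected to show a significant difference in time-to-treatment. Ease and feasibility are therefore what this pilot can best inform. With no benchmark set beforehand, the standard for a good enough result would be chosen after the data are seen, and a wide range of results could be read as support for the larger study.

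**Working it through.** **Inputs from the documents.** N = 30 and a predicted 20% with hypotension (III.2.a); 1:1 allocation, so 30/2 = 15 per group, and ClearSight on everyone (III.2.e); significance level 0.05 and Fisher's test as an option for proportions (III.4.b). The documents give no feasibility rate or pass mark, so the rates below are assumptions shown over a range.

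**The plan's own figure.** "A total of N=30 patients will be enrolled with a predicted 20% (n=6) experiencing hypotension events of interest": 30 × 0.20 = 6. This reproduces. No power, precision or threshold is stated for ease or feasibility, so there is no such figure to check.

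**Step 1: what the default test shows when both groups have the same feasibility p.** Let a and b be the numbers of yes answers out of 15 in each group. Then

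P(non-significant) = Σₐ Σ_b Bin(a; 15, p) × Bin(b; 15, p) × 1[Fisher two-sided P(a, b) ≥ 0.05].

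| True feasibility, both groups | P(non-significant) |
|---|---|
| 10% | 0.995 |
| 50% | 0.983 |
| 80% | 0.983 |
| 90% | 0.995 |
| 95% | 0.999 |

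The test behaves identically at 10% and 90%, as it must by symmetry. For the 0–10 ratings, a simulated Mann–Whitney test (4,000 runs, 15 per group, assumed SD 1.5, values rounded and limited to 0–10) rejected in 4.3% to 4.8% of runs at common means of 9, 8, 5, 3 and 2. It too says nothing about the level.

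**Step 2: when the groups differ.** At 90% versus 50%, the same enumeration gives a rejection probability of 0.54. Significance then shows a difference between groups, but still not that the device is usable.

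**Step 3: why the missing benchmark matters.** The exact (Clopper–Pearson) 95% interval for x of n runs from the 0.025 quantile of Beta(x, n−x+1) to the 0.975 quantile of Beta(x+1, n−x). For an observed 24/30 (80%) these are Beta(24, 7) and Beta(25, 6), giving 61.4% to 92.3%. The lower limit clears a 60% mark and misses a 70% mark, so the conclusion depends on a number the plan does not contain.

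**Step 4: can 30 patients support a benchmark?** Take an illustrative rule of at least 26 yes answers out of 30. The pass probability is Σ Bin(x; 30, p) for x = 26 to 30.

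| True feasibility | P(pass) |
|---|---|
| 70% | 0.030 |
| 90% | 0.825 (0.8245) |
| 95% | 0.984 |

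The chance of missing the mark at a true 90% is 1 − 0.8245 = 0.1755, about 18%. With only the 15 HPI patients, keeping the 70% pass rate below 5% needs at least 14/15 (0.035), and that passes a 90% device only 55% of the time. The full sample is therefore much the better basis.

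**Step 5: the denominator.** "Randomization will be 1:1 and occurs immediately after informed consent and signature for research activities", so a device failure can come to light after randomisation and then meet an exclusion in III.2.d. Suppose the device was tried in 30 patients, 6 could not use it, and the other 24 were rated yes. Counting everyone gives 24/30 = 80%; dropping the failures gives 24/24 = 100%.

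**The case against.** The strongest reply is that III.4.b commits to number and percentage for categorical data and median with interquartile range for ordinal data. A 50% and a 95% yes rate would look quite different in the report, and the sponsor could judge them. That stands. A reader might infer that the pilot cannot decide anything about usability; the documents do not support that. What is absent is a basis for the judgement fixed in advance, and an interval around the estimate.

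A reader might also infer that P<0.05 is the plan's continuation rule. It is not: it is a general significance convention that reaches this outcome by default, and no section ties it to expansion. Nor does any section make expansion conditional on feasibility. II.1 states an intent and III.2.a speaks of an estimate to inform continuance. The lack of a benchmark is thus a gap, not a contradiction.

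Third, a between-group contrast may be partly intended. II.1 frames the aim as ClearSight compared with the arm cuff, the nurse item refers to blood pressure monitoring in general, and Group CM is blinded to ClearSight output, so the groups' ratings could differ. This is a fair reason to report results by group. It does not turn the comparison into a measure of usability, because both groups wear both devices. It also means that the claim of the same test result at every level holds only when usability is similar in the two groups.

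Finally, the contents of the data collection form are not shown, so item wording and anchors cannot be checked. Nothing in III.4.b refers to a threshold there.

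**Conclusion.** The point holds in this form: the first primary outcome has no dedicated analysis, interval or pre-specified benchmark, and the between-group test that applies by default does not measure it. With equal rates and 15 per group, Fisher's test is non-significant at least 98% of the time at every feasibility level tabulated.

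The Fisher figures assume 15 evaluable patients per group, independent answers and equal rates in both groups; the rating simulation also assumes an SD. The benchmark figures are illustrative, because the documents supply none. The change should be made before enrolment, since a benchmark chosen after the data are seen does not close the gap.

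**What to change.** In III.4.b, add a primary analysis for ease and feasibility with four elements:

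1. **Estimate.** The proportion of nurse yes answers with an exact 95% CI, and the median patient and nurse ratings with CIs, overall and by group. Any between-group comparison is descriptive only.
2. **Benchmark.** A continuation value for the proportion and for the ratings, set by the sponsor before enrolment. The 26/30 rule (exact 95% CI at 26/30: 69% to 96%) only illustrates what 30 patients can support.
3. **Denominator.** All randomised patients in whom ClearSight was attempted. Inability to use the device and device-related incomplete data count as not feasible and are not removed under III.2.d. If the number attempted is not 30, the count in the rule is restated.
4. **Use.** The decision to expand refers to this benchmark, not to a P value.

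The cost is a paragraph in III.4.b and a matching clarification of III.2.d, with no extra patients. The outcome must also be recorded for device failures. The small downside is that the sponsor commits to a mark it could miss by chance: about 18% of the time at a true 90% under the illustrative rule.

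### The primary monitoring effect comes from a Cox model with unnamed covariates picked from the trial's own data, with about 6 events predicted; make a prespecified group-only model primary

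*Combined protocol and SAP*

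**What the plan says.** Under Primary Outcome Analysis (Survival Analysis), the SAP begins: "Single-variable proportional hazards regression models will be created for each potential covariate of interest". Covariates with univariate P<0.10 enter a multivariable model, and "the best-fit multivariable model will then be generated by removing variables with" P>0.05 in a backward stepwise fashion. The primary question is then assigned to a proportional hazards model to "assess the effect of the monitoring type, with effects of covariates controlled in the best-fit multivariable model". The time modelled is treatment-free time.

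The candidates are not named, counted or restricted to baseline. The test behind the P values (Wald or likelihood ratio) is not given. Nor does the SAP say whether group is kept in the model during selection. Time-to-event estimates with standard errors "for both groups will be calculated from the single-variable models", so an unadjusted summary is planned, but it is not the primary estimate.

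On size, III.2.b states: "A total of N=30 patients will be enrolled with a predicted 20% (n=6) experiencing hypotension events of interest". It also cites internal data that "approximately 20-30% of patients receiving ELA require treatment with a vasopressor within the first 4 hours of ELA initiation". Section III.2.a does not expect a significant difference, "but should yield an estimate of the potential differences for a continuance of study". Section III.2.e states: "Randomization will be 1:1 and occurs immediately after informed consent".

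**The concern.** With 1:1 randomisation, a valid comparison of the arms needs no covariate search. Searching by P value with so few events mostly selects chance associations, and each covariate kept moves the group HR.

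The statistical product expected of this pilot is an estimate to carry into a larger study. As written, that estimate is not unique. Two analysts who follow the SAP faithfully, but choose different candidate lists or different tests, can report different primary HRs from the same 30 patients. The CI takes no account of the search.

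The open list also admits variables that arise after ELA initiation. The Electronic Health Record Variables list includes total vasopressor doses, which partly record the outcome itself.

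**Working it through.** **Event count.** The plan's figure is reproduced: 30 × 0.20 = 6. At the upper internal rate, 30 × 0.30 = 9. The modelled event is first treatment, not hypotension. HPI alerts (Hypotension Treatment Protocol) and the usual systolic and fetal-heart-rate criteria (Hypotensive Event Measurement) can also lead to treatment, so 30 × 0.40 = 12 was added as an assumption.

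**Number of candidates.** The SAP gives none, so 5 and 10 were assumed, all pure noise. Ten of the 18 variables in the Electronic Health Record list are known before or at ELA initiation (age to pre-ELA pain score). That list is for data collection; it is not a candidate list.

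**Precision without covariates.** With equal arms, SE(log HR) ≈ 2/√events, and the 95% CI factor is exp(1.96 × SE):
- 6 events: exp(1.96 × 0.816) = 4.95
- 9 events: exp(1.96 × 0.667) = 3.69
- 12 events: exp(1.96 × 0.577) = 3.10

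The simulated factors are slightly wider, at about 5.5, 3.9 and 3.2.

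**Simulation of the SAP rule.** Settings: 15 per arm, exponential times, censoring at 4 h, no group effect, 10,000 trials per setting, and covariates either all continuous or 40% binary. Covariates entered at univariate P<0.10 and were removed backward at P>0.05; group was then added to those retained. Wald and likelihood-ratio (LR) selection were run on the same data. The 5-item list is the first five of the ten.

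| | ~6 events | ~9 events | ~12 events |
|---|---|---|---|
| SD of log HR, group only | 0.80-0.81 | 0.73 | 0.63 |
| SD, one prespecified covariate | 0.86-0.88 | 0.76-0.77 | 0.66 |
| SD, selected from 5 | 0.84-0.87 | 0.74-0.75 | 0.64-0.65 |
| SD, selected from 10 | 0.87-0.94 | 0.77-0.79 | 0.65-0.67 |
| 5-item vs 10-item list: HR >1.5-fold apart | 6-11% | 6-9% | 5-6% |
| One arm without events (excluded) | 6.5-7.0% | 0.9-1.0% | 0.1% |

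Across the three event levels:
- **Noise covariate kept:** 15-23% of trials (5 candidates) and 27-41% (10) with Wald selection; 25-28% and 44-49% with LR.
- **5-item versus 10-item list, same data:** a different primary model in 15-28% of trials.
- **Wald versus LR, same data and list:** a different model in 4-28%; HR more than 1.5-fold apart in 1-6%.
- **Selected HR more than 1.5-fold from group-only:** 4-11% (5 candidates) and 9-20% (10), against 3-7% with one prespecified covariate.
- **No finite fit after selection:** 0.1% or less with Wald. With LR and binary candidates it was 9-16%, 3-5% and about 1% at 6, 9 and 12 events; these were excluded from the HR comparisons.

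**What selection itself costs.** At 6 events the SD rises 4-9% (5 candidates) or 8-18% (10) over group-only. One prespecified covariate costs 8%. Selection therefore adds nothing clear with five candidates and at most about 18 - 8 = 10 percentage points with ten.

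**Bias and type I error.** With a true HR of 2 (8,000 trials per setting), mean log HR stayed within 0.03 of group-only, and the list dependence was similar (HR more than 1.5-fold apart in 5-12%). Type I error was 0.9-4.2% (Wald) and 2.8-5.7% (LR), against 0.7-3.7% and 2.2-5.2% for group-only. A separate simulation with LR tests and 10-18 candidates gave 7.5-13.8%. The answer depends on test and candidate count, so no inflation is claimed.

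**The case against.** The strongest reply is that the harm is small against the imprecision. A 1.5-fold shift in 5-11% of trials sits inside a CI of x/÷3.2 to 5.5 that the change barely narrows. That is correct, and it limits the priority of the point.

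First treatments may also exceed 12. If 25% of the conventional arm and 60% of the HPI arm were treated (about 13 events), or 30% and 80% (about 17), selection raises the SD of log HR by only 1-4%, and the selected HR is more than 1.5-fold from group-only in 2-8% of trials. Those shares are assumed, since the documents give none, but the direction stands: more events, less harm.

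This is a pilot with several primary outcomes, and no go/no-go rule or sample-size formula uses the HR. That stands too, but III.2.a still expects the pilot to supply an estimate, and it should be a defined one. The planned single-variable summaries help, yet the SAP gives the primary question to the selected model.

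One named baseline covariate would also cure the lack of prespecification, and chance imbalance with 15 per arm is a fair reason to adjust. Group-only is therefore a choice, made because it spends the fewest parameters on about 6 events. It does not defend a P-value search.

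Finally, the Electronic Health Record list records event start to treatment, while the SAP models treatment-free time, which in the HPI arm can end at an alert before any hypotension. That needs settling separately, and this change does not settle it.

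**Conclusion.** The concern holds. The SAP states a rule that makes the primary HR depend on chance selection and on two open choices, the candidate list and the test. Under the assumed 5 to 10 noise candidates and about 6 to 12 events, the list alone changes the primary model in 15-28% of trials and moves the HR more than 1.5-fold in 5-11%. The loss of precision attributable to selection itself is modest: nothing clear with five candidates, at most about 10 points of SD with ten.

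The sizes rest on the assumed candidate number, noise-only covariates and event shares, and they shrink as first treatments increase. The finding that the estimate is not uniquely defined rests on the SAP text alone. The change should be made, but it will not make the pilot estimate precise.

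**What to change.** In III.4.b, Primary Outcome Analysis:

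- Make the primary estimate a prespecified Cox model with monitoring group as the only term. Report the HR with 95% CI, Kaplan-Meier curves and event counts by arm.
- State a sparse-data method, for example a Firth-penalised fit, for the case in which one arm has no events.
- Label any covariate-selected model exploratory, name its candidates and the test used, and limit the candidates to variables measured before ELA.

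This costs SAP wording only, with no new data. The downside is that covariate associations leave the primary analysis, and any gain from adjusting for a strongly prognostic covariate will be seen only in the exploratory model.

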### ***Blood Pressure Monitoring and Hypotension treatment protocol is standardized as below.***

#### **BP MONITORING PROTOCOL**

Group CM	Group HPI
-----------------	------------------

<math>T_0</math> At the time of test dose delivery, automated NIBP cycles will begin q3min for 30 minutes, amounting to a total of at least 10 blood pressure measurements.
 
<math>T_{30}</math> After 30 minutes, NIBP cycles to q15min per existing clinical standards
 
<math>T_{4\text{hours}}</math> Monitoring for research ends
	
<math>T_0</math> At the time of test dose delivery, Clearsight monitoring continues.
 
<math>T_0 - T_{4\text{hours}}</math> ClearSight monitoring is continuous
 
<math>T_{4\text{hours}}</math> Monitoring for research ends

--	--

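### The primary time-to-treatment result is a single hazard ratio, which on a clock from ELA mainly tracks how many patients are treated and not how many minutes are saved

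*Combined protocol and SAP*

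**What the plan says.** Section I states the hypothesis as a reduction in time-to-treatment, and III.2.c lists that outcome in minutes. In III.4.b, Primary Outcome Analysis, treatment-free time is the response and "a proportional hazards model will be used to assess the effect of the monitoring type", adjusted for covariates kept by backward selection. The time origin is not stated. No check of proportionality, time-varying effect or time-scale summary is planned as the primary estimate. Group time-to-event estimates with standard errors are promised, but they come from the single-variable proportional hazards models.

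The electronic health record list offers another clock: "Time of hypotensive event start to time of treatment for hypotension".

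In the BP Monitoring Protocol for Group CM, "automated NIBP cycles will begin q3min for 30 minutes"; then "After 30 minutes, NIBP cycles to q15min per existing clinical standards". For Group HPI, "ClearSight monitoring is continuous". Group HPI is also treated on alerts at an index of 75, and the Background cites prediction 5 to 15 min ahead. Unneeded treatment after a false positive is a listed risk. Section III.2.a expects 6 hypotensive patients among 30. It does not expect significance, but it does expect an estimate of the difference to carry into further study.

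**The concern.** A monitor that warns earlier moves treatments forward by some minutes. It does not multiply the treatment rate by a constant over four hours. If the same patients are treated in both groups, Group HPI has more treatments early and fewer late, and one HR averages these to something close to 1. If Group HPI also treats patients who would not have become hypotensive, the HR rises because more patients are treated, whether or not anyone is treated sooner.

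The pilot's product on this outcome is the estimate for the next study. An HR near 1 could be read as no benefit when treatment was faster. An HR of 1.5 could be read as faster treatment when it was only more treatment. Neither gives the minutes saved.

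**Working it through.** **Inputs from the documents.** N = 30, 20% hypotensive, 1:1 allocation, 4 h of monitoring; cuff every 3 min to T30, then every 15 min; ClearSight continuous; lead of 5 to 15 min.

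**The plan's own figures.** 30 × 0.20 = 6 hypotensive patients, as stated, so about 3 per group. 30 min / 3 min = 10 cuff readings, also as stated. No HR, power or target number of events is given.

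**Step 1: what one HR measures on the ELA clock.** With constant proportionality, the HR equals the ratio of cumulative hazards at 4 h, ln(1 − share treated in HPI) / ln(1 − share treated in CM). The timing of treatment within the 4 h does not enter. Assume all hypotensive patients (20%) are treated in both groups, and vary the extra alert-driven treatment among the 80% who are not hypotensive:
- none: ln(0.80)/ln(0.80) = 1.00
- 8%: share 0.20 + 0.80 × 0.08 = 0.264; ln(0.736)/ln(0.80) = 0.3065/0.2231 = 1.37
- 13%: share 0.20 + 0.80 × 0.13 = 0.304; ln(0.696)/ln(0.80) = 0.3624/0.2231 = 1.62

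**Step 2: simulation (400,000 per group, Cox fit with group only).** Assumptions not in the documents: onset exponential (mean 10, 20, 40 or 90 min) or uniform over 4 h; CM treated at the first cuff reading at least 1 min after onset; HPI treated 1 min after onset (no lead) or 5, 10 or 15 min before it. Selected results with equal shares treated:

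| Onset | Lead (min) | CM mean delay (min) | HR overall | HR before T30 | HR after T30 |
|---|---|---|---|---|---|
| mean 40 | 5 | 5.6 | 1.03 | 1.16 | 0.88 |
| mean 40 | 15 | 5.6 | 1.04 | 1.38 | 0.69 |
| mean 90 | none | 6.9 | 1.00 | 1.00 | 1.00 |
| mean 90 | 15 | 6.9 | 1.03 | 1.48 | 0.84 |
| uniform | none | 7.7 | 1.01 | 0.97 | 1.02 |
| uniform | 15 | 7.8 | 1.03 | 1.58 | 0.95 |

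Across all settings with equal shares:
- The overall HR is 1.00-1.07, with treatment about 3 to 23 min earlier on average.
- If CM needs two consecutive low readings, the HR is 1.02-1.10. The top of that range arises partly because some late CM episodes are not confirmed by 4 h (18.8% v 20.0% treated).
- With extra alert-driven treatment, the HR is 1.38-1.46 (8%) and 1.64-1.73 (13%), close to the hand calculation.

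**Step 3: source of the non-proportionality.** With a 5-15 min lead, the HR is 1.09-1.58 before T30 and 0.21-1.00 after it. With no lead and the cuff change in place, it is 0.97-1.03 and 1.00-1.02. The lead therefore drives the reversal. The two-reading variant with no lead departs modestly when onsets are very early (mean 10 min: 1.06, then 0.84).

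**Step 4: what the cuff change does.** Mean wait to the next reading = interval/2: 3/2 = 1.5 min before T30 and 15/2 = 7.5 min after it. Requiring 1 min of hypotension gives simulated delays of about 2.5 and 8.5-10.4 min. With 3 CM episodes, moving one across T30 changes the CM mean by (7.5 − 1.5)/3 = 2 min.

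**Step 5: the other clock.** From onset, in hypotensive patients only, with 1 min detection in HPI and an assumed 2 min mean reaction in both groups, the HR is 2.1-6.6. Mean delays are 4.9-9.8 min in CM and 3.0 min in HPI.

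**Step 6: precision.** A 3 v 3 permutation test has 20 arrangements, so the smallest two-sided P is 2/20 = 0.10 and a 95% permutation interval is unbounded. With 6 events, the HR detectable at 80% power (Schoenfeld) is exp(√(4 × (1.96 + 0.8416)² / 6)) = exp(2.287) = 9.85.

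**The case against.** The strongest defence is that this is a pilot with about 6 events. It cannot tell an HR of 1.00 from 1.10, and it does not claim to show a difference. The onset distributions and extra-treatment rates are invented. The simulated CM group also leaves out the usual clinical triggers (systolic pressure and fetal heart rate) that stay in force. Some time-scale reporting is likely anyway, because onset-to-treatment time is collected and the general descriptive plan would cover it. Finally, comparing delays conditions on hypotension, which arises after randomisation; treatment-free time in all randomised patients avoids that.

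Much of this stands. The simulated HRs illustrate a mechanism and do not forecast this trial's result. The selection problem is real, and a delay comparison needs an all-randomised summary beside it. The defence does not settle which number the pilot hands on. The only model named for the primary comparison yields an HR, and with about 20% treated the median treatment-free time from ELA would not be reached in 4 h.

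A reader might go further and infer that the 3-to-15-minute cuff change by itself makes the hazards non-proportional. Step 3 does not support that: without a lead, and with one low reading needed, both periods stay near 1.

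**Conclusion.** The point holds as a mismatch between the question and the effect measure. On the ELA clock, the HR follows the share treated: about 1.00-1.10 with equal shares, about 1.4-1.7 with 8-13% extra alert-driven treatment. With a 5-15 min lead and equal shares it is above 1 before T30 and mostly below 1 after it. The cuff change matters for a different reason: CM's mean wait is five times longer after T30 (7.5/1.5), so a pooled delay depends on when episodes fall.

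It would be too strong to say that the HR must stay near 1 even if HPI works. That needs both the ELA clock and equal shares treated. The SAP does not state the origin, alerts can raise the share treated in Group HPI, and on the onset clock the HR is well above 1. The same device benefit can thus give very different HRs depending on choices the plan leaves open.

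All HRs rest on assumed onset times, leads and alert rates. The cited sensitivity and specificity describe predictions, so 8% and 13% as patient-level rates are assumptions. The change should be made before analysis, since six events cannot usefully test proportionality.

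**What to change.** In III.4.b:
- Make the primary time-to-treatment estimate the between-group difference in minutes from hypotension onset to first treatment, using the interval already collected.
- Use one onset rule for both groups, for example the ClearSight record that all participants wear. At present the Hypotensive Event Measurement section uses the cuff in CM and ClearSight in HPI. Dating CM onset by the cuff would hide the wait for the next reading.
- Count treatment before onset as zero or negative delay, choosing one in advance. Report alert-driven treatment without hypotension separately.
- Show individual values and medians for episodes starting in 0-30 and 30-240 min, descriptively, without relying on a 95% permutation interval at about 3 episodes per group.
- Because that comparison conditions on hypotension, also report the cumulative proportion treated at 30 and 240 min in all randomised patients.
- Keep the Cox HR as a secondary description, with its time origin stated.

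The cost is SAP wording and a little extra tabulation, including reading onset from the stored ClearSight data. The downside is very few episodes per period, so these estimates will be imprecise.
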